## **STATEMENT OF COMPLIANCE**

The study will be conducted in compliance with this clinical study protocol, Good Clinical Practice (GCP) as outlined by International Council for Harmonisation (ICH) E6 (R2), and all applicable local regulations including US Code of Federal Regulations [CFR] Title 21 and with the ethical principles laid down in the Declaration of Helsinki. Enrollment at the clinical study site may not begin prior to receiving Institutional Review Board (IRB) approval of this protocol, the Investigator's Brochure (IB), and all patient facing materials (e.g., all advertising materials or materials given to the subject during the study).

Any amendments to the protocol and changes to the consent document must also be approved by the IRB before implementation of that amendment.

The Principal Investigator will ensure that changes to the study plan as defined by this protocol will not be made without prior agreement from the Sponsor and documented approval from the IRB of record, unless such a change is necessary to eliminate an immediate hazard to the study subjects.

HBI-8000 Tablet  
IND 078395

HUYABIO International, LLC  

## STUDY SYNOPSIS

Name of Sponsor/ Company:	HUYABIO International, LLC
Name of Finished Product:	HBI-8000 (tucidinostat)
Name of Active Ingredient:	N -(2-amino-4-fluorophenyl)-4-{{(2E)-3-(pyridin-3-yl)prop-2-enamido]methyl}benzamide
Title of Study:	A Phase 2 Study to Assess the Safety and Efficacy of HBI-8000 in Combination with Pembrolizumab for Advanced or Metastatic Non-Small Cell Lung Cancer (NSCLC)
Protocol No:	HBI-8000-305
Lead Investigator:	[name]
Indication	Advanced or Metastatic NSCLC
Study Population	Subjects $\geq 18$ years of age with advanced or metastatic NSCLC who have not received immune checkpoint inhibitor for their disease but have programmed death ligand 1 (PD-L1) expression Tumor Proportion Score (TPS): $\geq 1\%$ .
Study center(s):	Multicenter study (US): 6-10
Study duration:	Approximately 38 months (including follow-up)  The study will include a screening period (up to 28 days), up to 24 months of treatment of HBI-8000 with pembrolizumab, up to 1 month post-treatment follow-up for safety, and up to 12 months after the last dose of HBI-8000 for survival follow-up by telephone calls/e-mails.
Phase	2
Study Treatment	HBI-8000 tablets 30 mg/dose, orally twice a week  An HBI-8000 treatment cycle consists of twice a week dosing over 21 consecutive days. Pembrolizumab will be administered at 400 mg every 6 weeks or 200 mg every 3 weeks according to Prescribing Information and institutional practice.  Treatment will continue until disease progression or unacceptable toxicity occurs. Should toxicity be deemed not related to pembrolizumab but HBI-8000, subject may continue to receive pembrolizumab under standard of care. Should toxicities be deemed related to pembrolizumab, the subject may continue receiving HBI-8000 at the discretion of Investigator.
Objectives:	
Primary:
 

To evaluate the efficacy of HBI-8000 in combination with a standard dose and regimen of pembrolizumab as a first line checkpoint inhibitor therapy for advanced or metastatic NSCLC, as measured by Objective Response Rate (ORR) according to the Response Evaluation Criteria in Solid Tumors (RECIST) criteria version 1.1 [Eisenhauer 2009].

 
Secondary:
 

To evaluate the safety and tolerability of HBI-8000 in combination with a standard dose and regimen of pembrolizumab

To explore the additional efficacy parameters for HBI-8000 in combination with a standard dose and regimen of pembrolizumab as measured by Disease Control Rate (DCR), Duration of Response (DoR), and Progression-Free Survival (PFS)

Study design	This is a multicenter, open label, Phase 2 study of HBI-8000 in combination with a U.S. Food and Drug Administration (FDA) approved dose of pembrolizumab as a first line checkpoint inhibitor therapy for advanced or metastatic NSCLC where subjects must have programmed death ligand 1 (PD-L1) expression Tumor Proportion Score (TPS) $\geq 1\%$ .
Planned number of subjects:	20 to 24 subjects are planned for the study.
Diagnosis and main criteria for inclusion:	
Inclusion Criteria
 
Subjects may be entered in the study only if they meet all the following criteria:
 
 
1. Adults at least 18 years of age.
 
2. Eastern Cooperative Oncology Group (ECOG) performance status <math>\leq 2</math>.
 
3. Histopathologically confirmed diagnosis of NSCLC PD-L1 expression TPS <math>\geq 1\%</math> as determined by an FDA-approved test.
 
4. Have at least one measurable target lesion as defined by RECIST v.1.1.
 
5. Have not received immune checkpoint inhibitor therapy or more than one regimen of chemotherapy for advanced or metastatic disease. Subjects who have previously received immune checkpoint inhibitor therapy in the adjuvant or neoadjuvant setting may be allowed if disease progression occurred <math>>6</math> months after the last dose and no clinically significant immune related toxicities leading to treatment discontinuation were observed.
 
6. Prior adjuvant or neoadjuvant systemic therapy with chemotherapy, EGFR or ALK mutation directed therapy must have been completed <math>>4</math> weeks before Cycle 1 Day 1 (C1D1) dosing and recovered from all treatment related toxicity.
 
7. Any prior palliative radiotherapy or minor surgery must be completed at least 2 weeks and 1 week respectively before C1D1 dosing and recovered from all treatment related toxicities.
 
8. Adequate major organ functions at baseline as evidenced by laboratory findings within 14 days prior to C1D1 study drug administration as defined below: 
 
a. White blood cells (WBC) <math>\geq 3000/\mu\text{L}</math>, neutrophils <math>\geq 1500/\mu\text{L}</math>, platelets <math>\geq 100 \times 10^3/\mu\text{L}</math>, hemoglobin <math>\geq 9.0 \text{ g/dL}</math>, independent of transfusion.
 
b. Serum creatinine <math>\leq 1.5 \text{ mg/dL}</math>, normal electrolytes, phosphorus, and calcium.
 
c. Aspartate aminotransferase (AST) and alanine aminotransferase (ALT) <math>\leq 3 \times</math> upper limit of normal (ULN), alkaline phosphatase <math>\leq 2.5 \times</math> ULN unless bone metastases present, bilirubin <math>\leq 1.5 \times</math> ULN (unless known Gilbert's disease where it must be <math>\leq 3 \times</math> ULN) and serum albumin <math>\geq 3.0 \text{ g/dL}</math>.
 
d. Thyroid stimulating hormone (TSH) within normal limits.
 
 
 
9. Life expectancy <math>\geq 12</math> weeks.
 
10. A negative serum pregnancy test at baseline for women of childbearing potential (WOCBP).
 
11. Women of childbearing potential. (WOCBP), non-surgically sterile or premenopausal female capable of becoming pregnant and men (due to potential risk of drug exposure through the ejaculate) must agree to use an acceptable method of contraception while enrolled on this study, and for a period of 5 months following the last dose of treatment. Acceptable methods of birth control in this trial include 2 highly effective methods of birth control (as determined by the Investigator; one of the methods must be a barrier technique) or abstinence.
 
12. Have the ability to understand and the willingness to sign a written informed consent document.
 
 
Exclusion Criteria
 
Subjects who fulfill any of the following criteria at screening will not be eligible for admission into the study:
 
 
1. History of Grade <math>\geq 3</math> hypersensitivity reactions to monoclonal antibodies.
 


2. History of a cardiovascular illness including: QT interval corrected by heart rate using Fridericia's correction formula (QTcF) >450 ms in male or >470 ms in female, congenital long QT syndrome, congestive heart failure (New York Heart Association Grade III or IV) ([Appendix 2](#)); unstable angina or myocardial infarction within the previous 6 months; or symptomatic cardiac arrhythmia despite medical management.
3. Uncontrolled hypertension, systolic blood pressure (SBP) >160 mmHg or diastolic blood pressure (DBP) >100 mmHg.
4. Central nervous system metastasis or leptomeningeal disease except when treatment for brain metastasis is completed >14 days prior to C1D1 and stable for  $\geq 4$  weeks on <10 mg daily prednisone or equivalent.
5. History of hemorrhagic diarrhea, inflammatory bowel disease, active uncontrolled peptic ulcer disease or bowel resection that affects absorption of orally administered drugs.
6. Recurrent pleural effusion requiring repetitive palliative thoracentesis within 3 months prior to study entry, except for subjects with a pleurex port.
7. Active, known, or suspected autoimmune disease, or history of immune-mediated toxicity leading to treatment discontinuation, except for type I diabetes mellitus, hypothyroidism only requiring hormone replacement or skin disorders (such as vitiligo, psoriasis, or alopecia) not requiring systemic therapy.
8. Active pneumonitis, history of non-infectious pneumonitis that required treatment with steroids, or history of interstitial lung disease.
9. Active uncontrolled bacterial, viral, or fungal infection requiring systemic therapy.
10. Known history of testing positive for human immunodeficiency virus (HIV), known acquired immunodeficiency syndrome (AIDS).
11. Active hepatitis B (hepatitis B surface antigen [HBVsAg] positive), or hepatitis C (HCV antibody test or serum hepatitis C ribonucleic acid [RNA] positive).
12. Received approved live vaccines within 30 days of planned C1D1. Inactivated viral vaccines or vaccines based on subviral component are allowed; however intranasal influenza vaccines (e.g., Flu-Mist) are not allowed. COVID-19 vaccination should be administered >7 days before C1D1.
13. Any condition requiring chronic systemic treatment with either corticosteroids (>10 mg daily prednisone equivalents) or other immunosuppressive medications, or steroids use within 14 days of study drug administration. Inhaled or topical steroids are permitted.
14. Use of other investigational agent (drug not marketed for any indication) within 28 days or at least 5 half-lives (whichever is shorter) before study drug administration.
15. Pregnant or breast-feeding women.
16. Second malignancy unless in remission for 2 years; subjects with non-melanomatous skin cancer, carcinoma in situ of the cervix treated with curative intent, or curatively treated prostate cancer with prostate-specific antigen (PSA) <2.0 ng/mL can be included.
17. Underlying medical conditions that, in the Investigator's opinion, will make the administration of study drug hazardous or obscure the interpretation of toxicity determination or adverse events.
18. Unwilling or unable to comply with procedures required in this protocol.

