- b. End-of-Treatment Safety Follow-Up visit, performed 30 ± 3 days after the last day of HBI-8000 administration, or before the initiation of new cancer treatment, whichever is earlier.
- c. Informed consent must be obtained prior to initiation of any study-specific procedures.
- d. Cancer diagnosis must include known mutation status for BRAF V600, EGFR, and ALK.
- e. Temperature, heart rate, diastolic and systolic blood pressure after subject is in a supine position for at least 5 minutes.
- f. Complete physical exam at baseline. Symptom directed physical exam for screening and all other cycles.
- g. Standard 12-lead ECG will be done using local standard procedures at Baseline and at End of Treatment Safety Follow-Up visits.
- h. MRI performed per institutional guidelines and practice, and if clinically indicated for subjects with documented brain metastasis.
- i. Historical data may be used to assess for eligibility. If historical data is not available, tumor tissue will be analyzed locally by an FDA-approved test to yield PD-L1 status prior to enrollment.
- j. Hematology panel to include hemoglobin, hematocrit, red blood cell count, white blood cell count, differential, platelet count.
- k. Chemistry panel to include BUN, creatinine, AST, ALT, LDH, total bilirubin (including direct fraction if total bilirubin abnormal), lipase, amylase, TSH, T4 free (direct), total protein, albumin, uric acid, alkaline phosphatase, sodium, potassium, calcium, magnesium, phosphorus, and glucose.
- l. Urinalysis: dipstick followed by microscopic examination, if abnormal results.
- m. For women of childbearing potential (including those with tubal ligation): Serum pregnancy test at baseline (within 14 days of starting treatment) and at the end of treatment.
- n. Hepatitis B and Hepatitis C testing to include HBsAg, anti-HCV antibodies.
- o. HBI-8000 should be administered twice a week approximately 30 minutes after a meal.
- p. Pembrolizumab 400 mg every 6 weeks or 200 mg every 3 weeks on Day 1 of each Cycle should be administered as intravenous (IV) infusion over 30 minutes and in accordance with the manufacturer package insert and institutional practice.
- q. Tumor assessment of all lesions by radiographic or other modality (CT, MRI). Tumor assessments to be performed at Screening, and Day 1 of Cycles 3, 5, 7, etc. every 6 weeks (± 3 days) thereafter until PD.

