13. Any condition requiring chronic systemic treatment with either corticosteroids (>10 mg daily prednisone equivalents) or other immunosuppressive medications, or steroids use within 14 days of study drug administration. Inhaled or topical steroids are permitted.
14. Use of other investigational agent (drug not marketed for any indication) within 28 days or at least 5 half-lives (whichever is shorter) before study drug administration.
15. Pregnant or breast-feeding women.
16. Second malignancy unless in remission for 2 years; subjects with non-melanomatous skin cancer, carcinoma in situ of the cervix treated with curative intent, or curatively treated prostate cancer with prostate-specific antigen (PSA) <2.0 ng/mL can be included.
17. Underlying medical conditions that, in the Investigator's opinion, will make the administration of study drug hazardous or obscure the interpretation of toxicity determination or adverse events.
18. Unwilling or unable to comply with procedures required in this protocol.

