### **5.4.1 Prohibited Medications and Therapy**

Concomitant administration of the following types of drugs and procedures is not allowed:

- Recently completed drug-drug interaction study showed a mild (approximately 40%) increase of AUC of HBI-8000 when itraconazole, a strong CYP3A4, was administered concurrently. The use of potent CYP3A4 inducers or inhibitors ([Appendix 3](#)) should be avoided.
- Live vaccines within 30 days prior to the first dose of trial treatment and while participating in the trial. Examples of live vaccines include, but are not limited to, the following: measles, mumps, rubella, chicken pox, yellow fever, seasonal flu (that contain a live virus), H1N1 flu, rabies, BCG, and typhoid vaccine.
- Surgery for tumor control or symptoms management is not permitted during the study.
- Concomitant administration of anti-tumor treatment other than the Study Treatment, or procedures that could interfere with the evaluation of safety or anti-tumor effect of Study Treatment, is prohibited during the study.

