### **6.1 Study Visits and List of Procedures**

#### **6.1.1 Screening Assessments (within 28 days prior to start of treatment)**

Written informed consent for participation in the study must be obtained before performing any study-specific screening tests or evaluations. Informed Consent Forms (ICFs) for all subjects screened will be maintained at the study site.

Screening assessments will be performed within 28 days prior to Day 1. Results of standard of care tests or examinations performed prior to obtaining informed consent and within 28 days prior to Day 1 may be used (and do not need to be repeated during screening unless they do not meet the criteria defined in the protocol).

The following will be collected or performed between Day -28 and Day -1:

- Written informed consent

- Inclusion/exclusion criteria review for confirmation of eligibility
- Medical history, concomitant medications, baseline signs and symptoms, demographics, and height
- HBsAg and anti-HCV serology tests
- Cancer diagnosis history including histological diagnosis, PD-L1 expression, known mutation status for B-Raf proto-oncogene serine/threonine kinase gene (BRAF) V600, EGFR, and ALK and treatment history
- Brain magnetic resonance imaging (MRI) if clinically indicated, and radiographic tumor assessment. If a subject has metal implants, a computerized tomography (CT) scan should be used instead of an MRI.

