**APPENDIX 4. RECIST V1.1 AND irRECIST**

Lesion Requirements and Response Criteria	
Lesion Measurement	Unidimensional
Baseline Lesion Size a	$\geq 10$ mm
Malignant lymph nodes b	For the lymph node (s) to be considered pathologically enlarged and measurable, a lymph node must be $\geq 15$ mm when assessed by CT scan
Baseline Lesion Number	5 lesions total, 2 per organ
Appearance of New Lesions	Always represents PD
Response	CR: disappearance of all lesions
	PR: $\geq 30\%$ decrease from baseline STD
	SD: when neither PR nor PD can be established
	PD: $\geq 20\%$ increase in nadir of STD (minimum 5 mm)
Confirmation after first assessment	Yes, if response is primary endpoint

Abbreviations: CR = complete response; PD = progressive disease; PR = partial response; RECIST = Response Evaluation Criteria in Solid Tumors; SD = stable disease; STD = sum of target lesion(s) diameter(s).

a CT: 10 mm (when slice thickness is  $\leq 5$  mm); or 2 $\times$  slice thickness (when slice thickness is  $>5$  mm), Clinical: 10 mm (must be measurable with calipers)

b Lymph node:  $\geq 15$  mm short axis for target,  $\geq 10$  to  $<15$  mm for non-target,  $<10$  mm is non-pathological

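### Exclusion 14 can leave under 28 days' washout, and nothing requires the baseline scan to follow the last dose of an earlier investigational agent, so that agent's shrinkage could count in the ORR

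*Combined protocol and SAP*

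**What the plan says.** Exclusion 14 has the same wording in the Synopsis and in section 4.2, so it is not a slip in one place. It covers "Use of other investigational agent (drug not marketed for any indication") and sets the interval as "within 28 days or at least 5 half-lives (whichever is shorter) before study drug administration".

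On the timing of the baseline scan:
- Section 6.1.1: "Screening assessments will be performed within 28 days prior to Day 1". Standard-of-care results "performed prior to obtaining informed consent and within 28 days prior to Day 1 may be used".
- Table 1, footnote q: "Tumor assessments to be performed at Screening, and Day 1 of Cycles 3, 5, 7, etc". Neither place links the screening scan to the end of earlier therapy.
- Appendix 4 defines partial response as a 30% or greater "decrease from baseline STD", where STD is the sum of target lesion diameters.

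On other prior or concurrent treatment:
- Inclusion 6: "Prior adjuvant or neoadjuvant systemic therapy with chemotherapy, EGFR or ALK mutation directed therapy must have been completed" more than 4 weeks before C1D1, with recovery from all toxicity of that treatment.
- Inclusion 5 limits prior checkpoint inhibitors and chemotherapy for advanced disease. It does not address other classes of agent.
- Section 5.4.1 prohibits "Concomitant administration of anti-tumor treatment other than the Study Treatment" during the study. It gives no start date for this ban, although the live-vaccine item in the same list has an explicit window before first dose.

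**The concern.** ORR is the primary objective, the trial has one arm, and 20 to 24 subjects are planned. Every change in tumor size after the baseline scan is read as the effect of HBI-8000 plus pembrolizumab. That reading needs a baseline taken after earlier anticancer treatment has stopped. A gap of at least 28 days would secure this, because no scan may be older than Day -28. Taking the shorter of two intervals loses that guarantee for agents with short half-lives, and no separate rule on scan timing restores it.

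The plan is also uneven. Inclusion 6 asks for more than 4 weeks and recovery from toxicity after adjuvant or neoadjuvant chemotherapy, EGFR or ALK therapy. Exclusion 14 can ask for much less time after a drug with no marketing approval, and it does not mention recovery. A subject who received an investigational anticancer agent other than a checkpoint inhibitor or chemotherapy remains eligible under inclusion 5. Such a subject would not be removed from the FAS or PPS on eligibility grounds.

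**Working it through.** **The plan's own design figure.** Section 7.1 gives only the chance of seeing at least one adverse event of 10% incidence. 1 - 0.9^20 = 87.8% and 1 - 0.9^24 = 92.0%, as stated. This figure is sound and does not bear on the point. The plan gives no null ORR, power or alpha.

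**Washout under exclusion 14.** Washout = min(28 days, 5 × half-life). The two limbs meet at 28 / 5 = 5.6 days. The longest dosing period after a Day -28 scan is 28 minus the washout. The documents name no agents, so the half-lives are assumed:
- 12 hours: washout 2.5 days, up to 25.5 days of dosing after the scan
- 24 hours: 5 days, up to 23 days
- 48 hours: 10 days, up to 18 days
- 96 hours: 20 days, up to 8 days
- 5.6 days or more: 28 days, none

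**An allowed sequence.** Take an agent with a 24-hour half-life.
1. A standard-of-care scan is done on Day -28, before consent.
2. The agent is taken until Day -10.
3. Consent is signed on Day -9, and treatment starts on Day 1.

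The gap of 10 days exceeds the 5 days required, so exclusion 14 is met. The scan is within 28 days, so section 6.1.1 is met. The last dose precedes consent, so section 5.4.1 is not engaged. The agent has been given for 28 - 10 = 18 days after the baseline scan.

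**Effect on ORR.** One response moves ORR by 1/20 = 5.0 points or 1/24 = 4.2 points, assuming that all enrolled subjects enter the analysis set. The number of misattributed responses is not in the documents. For an assumed 0, 1 or 2, the shift is 0, 5.0 or 10.0 points at n = 20 and 0, 4.2 or 8.3 points at n = 24.

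**Against the planned exact 95% interval** (responder counts are illustrative):
- n = 20: 6/20 = 30.0% (11.9 to 54.3) becomes 7/20 = 35.0% (15.4 to 59.2)
- n = 24: 6/24 = 25.0% (9.8 to 46.7) becomes 7/24 = 29.2% (12.6 to 51.1)

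**The case against.** **Section 5.4.1 may already forbid this.** The Synopsis and section 3.1 count screening as part of the study, so on a natural reading other anti-tumor treatment is barred once a subject consents. A reader might infer from exclusion 14 alone that dosing up to a few days before C1D1 is plainly permitted. The documents do not support that. What stays clearly open is dosing between a reused pre-consent scan and consent, and only standard-of-care scans may be reused. The objection narrows the gap but does not close it. If 5.4.1 does cover screening, it also sits awkwardly with the short interval in exclusion 14.

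**A false response is not easy to obtain.** Appendix 4 calls for confirmation when response is the primary endpoint, although section 7.5.1 does not repeat this. Response scans are 6 weeks apart, so shrinkage from a stopped drug would have to reach 30% and last. This lowers the likelihood. It does not remove the route, because the confirming scan is compared with the same baseline. The error can also run the other way: a subject progressing on the earlier agent may grow between scan and C1D1, which lowers ORR.

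**Toxicity.** A reader might infer that the earlier agent's toxicity simply passes into the safety tables. It does not. Signs and symptoms present before treatment go to medical history, and an event is treatment-emergent only if it is new or worsens from first dose. Only new or worsened late effects would count.

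**Residual drug.** For half-lives above 5.6 days, drug can remain at C1D1 (25% after 28 days at a 14-day half-life), but no dose can then follow a scan within the window. Below 5.6 days, post-scan dosing is possible, but five half-lives leave only about 3%. The two effects concern different agents and should not be added together.

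**Precision.** The analysis is descriptive, and one response lies well inside the interval. This stands, and it limits the weight of the point.

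**Conclusion.** The gap is real but narrow. Exclusion 14 allows less than 28 days for half-lives under 5.6 days, the baseline scan may date from Day -28 and precede consent, and no text orders the scan after the last dose. Tumor change caused by an earlier agent could therefore enter the single-arm ORR, at 4.2 to 5.0 points per misattributed response.

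This needs an enrolled subject who took an active agent with a short half-life between scan and C1D1. The documents give no frequency, and it may be zero. They do not show that any response will be misattributed, or that the net bias is upward.

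It is also tempting to conclude that the longer of the two intervals should apply. The documents do not establish that. Five half-lives would be 70 days at a 14-day half-life and 105 days at 21 days, while the protocol's life-expectancy floor is 12 weeks (84 days). The length of a washout is a clinical judgement, and the endpoint can be protected without changing it. This is a cheap improvement, not a flaw that undermines the trial.

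**What to change.** - In section 6.1.1 and Table 1 footnote q, require the baseline tumor scan to be taken after the last dose of any prior anticancer agent, including investigational agents. This closes the dosing-after-scan route whatever the washout. It also covers the one chemotherapy regimen allowed for advanced disease, for which the criteria state no washout.
- Reconcile exclusion 14 (Synopsis and section 4.2) with inclusion 6 on washout and recovery from toxicity, and with section 5.4.1, stating when the ban on other anti-tumor treatment begins. The sponsor should settle the length of the washout.

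The cost is one sentence in two places plus the reconciliation. An occasional candidate will need the baseline scan timed later or repeated. The change does not deal with drug still present at C1D1 after a long half-life. Treatment history is already collected, so the SAP could list any such subjects at little extra cost.
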